First, for each observation, peripheral blood and/or bone marrow differentials should add up to 100%. Some sites may not record 0% to reflect uncounted cell types as instructed. Instead, the corresponding field may appear as missing or “ND” even though data collection procedures have been vigorously followed. Also, the differentials may not exactly add up to 100%. To correct this problem, each domain of the differentials was summed together.

If the total was between 98.5% and 101%, the missing values were assigned 0%. Otherwise, the observation was left as is and the record was also to be reported as a data issue.

Second, for the set of variables collected to derive peripheral blood or bone marrow differentials at each post-baseline visit through week 12 on B1871006, if a given set were still incomplete, a non-missing set of lab variables obtained ± 3 days from the scheduled visit was utilized to complete the derivation. For visits after week 12 (relative to first B1871006 dose) from B1871006 and B1871040, a non-missing set of lab variables obtained ± 7 days of the visit will be utilized to complete that post-baseline assessment. For B1871006, the last non-missing peripheral blood or bone marrow differentials collected at week 1 day 1 or up to 28 days prior to week 1 day 1 was used for baseline assessment. For example, if the bone marrow blast count was missing, the entire non-missing bone marrow assessment, not just the blast field, from another observation was used. Some data handling rules for data combination are specified below.

- Data combination is needed only when the full dataset is not available on a single day at a given visit. The full dataset includes peripheral blood differential for chronic phase, and both bone marrow and peripheral blood differentials for advanced phase. The extramedullary assessment when absent should not preclude the derivation, and when present should be taken into account per response criteria rules.

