- During the post-baseline data combination, for visits up to and including week 12 from B1871006, the ± 3 window will be applied to days 1 and 7 separately; for visits after week 12 (relative to first B1871006 dose) from B1871006 and B1871040, the ± 7 window will be based on day 7 only. The latest date will be used as the date of visit and the more conservative value will be taken if there is more than one measurement for a variable. For platelet counts, in case of multiple values, the lowest value will be taken. If any value falls above or below normal range, the out-of range value will be taken.

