Appendix 1. HEMATOLOGIC RESPONSE DEFINITIONS

Hematologic Responses	Definition

Return to Chronic Phase (RCP) (or CP for subjects with CP) Minor Hematologic Response (MiHR) (for Ph+ ALL subjects) Subjects had to meet all criteria
	
Disappearance of features defining accelerated and blast phases, but still in chronic phase as noted by:
 
 • <15% Blasts in both blood and marrow • <30% Blasts + promyelocytes in both blood and marrow • <20% Basophils in both blood and marrow (marrow not applicable for Ph+ ALL) • No extramedullary involvement other than liver/spleen

Accelerated Phase had to meet at least 1 criterion
	
 • 15-29% Blasts in blood or marrow • ≥30% Blasts + promyelocytes in blood or marrow • ≥20% Basophils in blood or marrow 
only applicable to advanced phase
 
 • Platelets <100x10⁹/L (not related to therapy)

Blast Phase had to meet at least 1 criterion
	
 • ≥30% blasts in blood or bone marrow • Extramedullary involvement other than liver/spleen

No Evidence of Leukemia (NEL) had to meet all criteria
	
 • WBC ≤ institutional ULN • 450 x10⁹/L > Platelets ≥20x10⁹/L • ANC ≥0.5x10⁹/L • <20% basophils in blood • No blasts or promyelocytes in blood • Myelocytes + metamyelocytes <5% in blood • No extramedullary involvement (incl. hepato- or splenomegaly) 
only applicable for advanced phase
 
 • ≤5% bone marrow blasts

Complete Hematologic Response (CHR) had to meet all criteria
	
 • WBC ≤ institutional ULN • Platelets <450 × 10⁹/L • <20% basophils in blood • No blasts or promyelocytes in blood • Myelocytes + metamyelocytes <5% in blood • No extramedullary involvement (incl. hepato- or splenomegaly) 
only applicable to advanced phase
 
 • ≤5% bone marrow blasts • ANC ≥1.0 × 10⁹/L • Platelets ≥100 × 10⁹/L

Overall Hematologic Response (OHR) had to meet at least 1 criterion
	
CHR +NEL +RCP + MiHR (if applicable)

Major Hematologic Response (MHR) (had to meet at least 1 criterion)
	
CHR +NEL

Abbreviations: ANC=absolute neutrophil count, ULN=upper limit of normal range, WBC=white blood cell count

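### SAP Section 7 gives three unranked rules for multiple platelet counts, and for chronic-phase CHR the lowest-count rule is never the conservative choice

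*SAP*

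**What the plan says.** SAP Section 7 (Handling of Missing Values) explains how a post-baseline hematologic assessment is completed from laboratory values taken on nearby days. The scope is limited: "Data combination is needed only when the full dataset is not available on a single day at a given visit". Three sentences then deal with repeated measurements:

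1. General rule: "the more conservative value will be taken if there is more than one measurement for a variable".
2. Platelet rule: "For platelet counts, in case of multiple values, the lowest value will be taken".
3. Range rule: "If any value falls above or below normal range, the out-of range value will be taken".

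Nothing says which sentence prevails when they disagree.

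SAP Appendix 1 supplies the criteria: "Complete Hematologic Response (CHR) had to meet all criteria". For every patient the platelet item is "Platelets <450 × 10⁹/L". The item "Platelets ≥100 × 10⁹/L" stands under a sub-heading restricting it to advanced phase. The same restriction covers the accelerated-phase item of platelets below 100 × 10⁹/L, which is further qualified as "not related to therapy".

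Duration of CHR in B1871006 patients is a listed efficacy endpoint (SAP Section 6.1). CHR percentages and confirmed losses are summarised in SAP Section 8.2.1.

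**The concern.** A chronic-phase patient cannot fail the CHR platelet criterion by having a low count; only a high count fails it. For that criterion, then, the lowest of several counts is the value most favourable to response, which is the opposite of what the general rule asks for one sentence earlier.

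Two things are at stake. First, programmers who give priority to different sentences can classify the same visit differently. Second, if the platelet sentence is followed literally, a visit with one count below 450 and one at or above it is scored as meeting the criterion. That can credit CHR or conceal a non-response. Apart from confirmation by progression or death, loss of hematologic response needs two consecutive non-responses 14 or more days apart (SAP Section 6.1), so one visit scored as a response breaks the sequence. With six-monthly site visits for B1871006 patients (Protocol Section 6.2), recorded loss for such a patient could move by about one visit interval, unless an unscheduled test fills the gap.

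**Working it through.** The plan gives no figure to reproduce. The check is one of logic, followed by an illustration.

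**Inputs from the documents.** Chronic-phase CHR: platelets < 450. Advanced-phase CHR: 100 ≤ platelets < 450. NEL (no evidence of leukemia): 20 ≤ platelets < 450. All are × 10⁹/L, from SAP Appendix 1. The three rules are from SAP Section 7.

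**Assumption.** The documents state no normal range for platelets. I take a lower limit of 150 and try upper limits of normal (ULN) of 350, 400 and 450.

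**Step 1: direction.** Take every pair of different counts from 10 to 1000 in steps of 10. That is 100 values and 100 × 99 / 2 = 4950 pairs. Compare the status given by the lowest count with the status given by the other count.

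- Chronic-phase CHR: 44 values lie below 450 and 56 at or above it. The lowest count is more favourable in 44 × 56 = 2464 pairs, less favourable in 0, and neutral in 4950 − 2464 = 2486.
- Advanced-phase CHR: 35 values satisfy the criterion and 9 lie below 100. More favourable in 35 × 56 = 1960, less favourable in 9 × 35 = 315, neutral in 2675.
- NEL: more favourable in 43 × 56 = 2408, less favourable in 1 × 43 = 43, neutral in 2499.

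These counts show direction on an even grid. They are not frequencies in patients.

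**Step 2: the three rules on chronic-phase examples.**

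| Counts | Lowest | Conservative | Out-of-range |
|---|---|---|---|
| 380, 520 | 380, met | 520, not met | 520, not met (ULN 400 or 450); both out of range, no single answer (ULN 350) |
| 300, 500 | 300, met | 500, not met | 500, not met (all three ULNs) |
| 90, 500 | 90, met | 500, not met | both out of range, no single answer |
| 300, 340 | 300, met | 340, met | neither out of range; status unchanged |

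The rules disagree on CHR status only when the counts lie on both sides of 450.

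**Step 3: how far apart the rules can be at one visit.** Assume two independent normal counts with true mean μ and coefficient of variation CV (not given in the documents). Let p = Φ((450 − μ)/(CV × μ)). Then P(lowest < 450) = 1 − (1 − p)² and P(highest < 450) = p².

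- μ = 450, any CV: p = 0.5, giving 0.75 and 0.25.
- μ = 470, CV 8%: SD = 37.6, z = −20/37.6 = −0.53, p = 0.297, giving 1 − 0.703² = 0.51 and 0.297² = 0.09.

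These are single-visit, near-threshold cases. They do not estimate a change in the CHR rate or in its duration.

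**The case against.** The strongest reply is that the three sentences run in order, with the last as an override. The pair 380 and 520 then gives 520, CHR not met, provided 380 is in range and 520 is above it, and most of the bias disappears. What would remain is pairs with no single out-of-range value, such as two counts above the ULN on either side of 450, or one low and one high count. This is a fair reading, but the SAP does not state it. On that reading the platelet sentence has little left to do, so the text still needs reconciling.

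A reader might also infer that the rule always favours response and hides rising platelets throughout the chronic-phase cohort, which is 570 − 164 = 406 of 570 treated B1871006 patients, or 71% (Protocol Section 1.2.2). The documents do not support that, for four reasons:

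- The rule is neutral unless counts straddle 450.
- In advanced phase the lowest count can be the conservative one.
- The 71% describes patients, not affected visits. Chronic-phase assessment needs only a blood differential, whereas advanced phase needs blood and marrow, so combination is likely to be needed more often in advanced patients.
- Routine hematology for B1871006 patients is six-monthly in the extension, so several counts within ±7 days would generally come from repeat or unscheduled tests.

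Two further points stand. CHR also depends on other criteria and on confirmation (SAP Section 6.1). PFS uses investigator-assessed progression recorded as the reason for discontinuation, so this rule does not derive it.

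**Conclusion.** The point holds in limited form. SAP Section 7 contains three unranked rules that can give different answers. One of them, the lowest-count rule, is never the conservative choice for chronic-phase CHR and conflicts with the SAP's own general principle. This rests only on the SAP text and Appendix 1; the conflict with the range rule also depends on where the ULN lies.

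The size cannot be computed. It is bounded by the number of post-baseline visits that need data combination and have platelet counts on both sides of 450. That number is not given and is probably small. A material upward bias in CHR rate or duration is therefore possible but not shown. There are no hypotheses or decision rules (SAP Section 4), so no error rate is affected. The consequence is confined to descriptive hematologic summaries and to the reproducibility of the derivation.

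**What to change.** Replace the platelet sentence and, as it applies to platelets, the out-of-range sentence with:

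> For platelet counts, use the value least favourable to the criterion being assessed: the highest value for an upper limit (<450 × 10⁹/L) and the lowest value for a lower limit (≥100 × 10⁹/L for advanced-phase CHR; ≥20 × 10⁹/L for NEL).

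The limit of 20 is tied to NEL because in Appendix 1 it sits outside the advanced-phase sub-heading.

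Apply the rule to the combined B1871006 and B1871040 derivation, and report how many visits and how many CHR statuses change from the parent-study derivation.

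The edit to the text is small, but the cost is more than wording. SAP Section 7 describes the B1871006 hematologic handling as already carried out, so those data must be re-derived. CHR rate or duration may fall slightly and may differ from figures already reported, such as the 85.0% cumulative CHR in second-line chronic phase (Protocol Section 1.2.2). The count of changed statuses would explain any such difference.

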8. STATISTICAL METHODOLOGY AND STATISTICAL ANALYSES

8.1. Statistical Methods

8.1.1. Analyses of Continuous Data

For continuous variables, the descriptive statistics include n, mean, median, standard deviation (SD), and range (minimum, maximum).

8.1.2. Analyses of Categorical Data

For categorical variables, the descriptive statistics include the count in each category, the total n, and percentage.

8.1.3. Analyses of Binary Endpoints

Exact 2-sided 95% CIs will be provided for molecular, cytogenetic, and hematologic response rates.

8.1.4. Analyses of Time-To-Event Endpoints

For time-to-event endpoints such as DOR, time to transformation, PFS, and OS, the method of analysis will either be Kaplan-Meier (K-M) or cumulative incidence of the event adjusting for the competing risk of treatment discontinuation due to any reason without the event (Gray).¹

When applying the K-M method, medians and quartiles with the associated 2-sided 95% CI will be provided. The CIs are based on the Brookmeyer-Crowley linear transformation method will be provided. The K-M yearly rates with the associated 2-sided 95% CI based on Greenwood's formula will also be provided.

When applying the cumulative incidence method, yearly rates with the associated 2-sided 95% CI based on the delta method using a log transformation will be provided.

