A total of 164 patients with advanced Ph⁺ leukemia were enrolled and treated in B1871006. The primary population for the efficacy response analyses was the evaluable population, which included all patients with an adequate baseline assessment for the respective endpoint. In AP CML patients in the evaluable population (n=69), the confirmed overall hematologic response (OHR) rate by Week 48 was 55.1%. In BP CML patients in the evaluable population (n=60), the confirmed OHR rate by Week 48 was 28.3%.

Summary safety data across all patient cohorts in B1871006 showed most patients (560, 98%) reported at least 1 drug-related treatment-emergent adverse event (TEAE). Treatment-related TEAEs reported in ≥10% of patients were diarrhea in 454 (80%) patients, nausea in 238 (42%) patients, vomiting in 195 (34%) patients, thrombocytopenia in 167 (29%) patients, rash in 157 (28%) patients, abdominal pain in 97 (17%) patients, alanine aminotransferase (ALT) increased in 91 (16%) patients, anemia, fatigue, and neutropenia in 81 (14%) patients each, abdominal pain upper in 76 (13%) patients, and aspartate aminotransferase (AST) increased in 71 (12%) patients.

Treatment-related TEAEs of Grade 3 or higher included thrombocytopenia in 117 (21%) patients, neutropenia in 58 (10%) patients, diarrhea in 44 (8%) patients, ALT increased in 36 (6%) patients, and rash in 32 (6%) patients.

As of February 15, 2012, 134 (23.5%) patients have permanently discontinued bosutinib treatment because of AEs. The most frequent AEs that led to discontinuation were thrombocytopenia (26 patients, 4.6%), ALT increased (11 patients, 1.9%), neutropenia (8 patients, 1.4%), diarrhea and vomiting (7 patients, 1.2% each).

First-Line CP CML

In the Phase 3 study 3160A4-3000-WW (B1871008), bosutinib was compared to imatinib in the frontline treatment of CP Ph⁺ CML. The primary objective of the study was to compare the complete cytogenetic response (CCyR) at one year in CP patients receiving bosutinib alone versus patients receiving imatinib alone. The study enrolled 502 pts (250 on bosutinib

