4.2. Statistical Decision Rules

There are no statistical decision rules for this study and no adjustments for multiple comparisons. Confidence intervals (CI) are intended for descriptive purposes only.

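### SAP 8.1.4 names no transformation for the Greenwood intervals on K-M yearly rates and makes Brookmeyer-Crowley linear; plain Greenwood intervals under-cover in small subsets, near 0 or 100%, or under heavy censoring

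*SAP*

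**What the plan says.** SAP 8.1.4 sets three interval methods.

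- **K-M yearly rates:** "K-M yearly rates with the associated 2-sided 95% CI based on" Greenwood's formula. No transformation is named.
- **K-M medians and quartiles:** "The CIs are based on the Brookmeyer-Crowley linear transformation method will be provided". Here the linear scale is explicit.
- **Cumulative incidence:** "yearly rates with the associated 2-sided 95% CI based on the delta method using a log transformation". Here the transformation is explicit.

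SAP 8.2.1 uses K-M for overall survival, for PFS (alongside cumulative incidence) and, conditionally, for duration of response among responders. Time to transformation uses cumulative incidence only, so this point does not reach it. SAP 8.2 analyses efficacy by cohort, and Protocol 9.2 calls for presentation by disease stage and line of therapy.

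On the standing of the intervals, SAP 4.2 says: "Confidence intervals (CI) are intended for descriptive purposes only".

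Protocol 1.2.2 gives the sizes of the advanced groups: "A total of 164 patients with advanced" Ph+ leukemia; "In AP CML patients in the evaluable population (n=69), the confirmed overall hematologic response (OHR) rate by Week 48 was 55.1" percent; and "In BP CML patients in the evaluable population (n=60), the confirmed OHR rate by Week 48 was 28.3" percent.

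**The concern.** Greenwood's formula gives a variance. Adding and subtracting 1.96 standard errors on the survival scale yields a symmetric interval for a quantity that is bounded and skewed when few patients are at risk. Such intervals tend to be too short near 0 and 1 and can pass those bounds. Advanced-phase subsets and late yearly rates are where this would show.

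The study tests no hypotheses, so the intervals are its main formal statement of precision for long-term survival and response duration. There is also an inconsistency within one endpoint: PFS is reported by both K-M and cumulative incidence, so on the natural reading its two sets of intervals would be built on different scales.

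**Working it through.** The documents state no coverage figure, so there is none to reproduce; the benchmark is the nominal 95%.

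**Inputs from Protocol 1.2.2**

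- Accelerated phase: n=69. Responders by Week 48: 0.551 × 69 = 38.
- Blast phase: n=60. Responders by Week 48: 0.283 × 60 = 17.
- Remaining advanced patients: 164 − 69 − 60 = 35.

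**Assumed, because the documents do not give them:** true survival-type rates S, exponential event and censoring times, and the amount of censoring.

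**Formulas.** With K-M estimate s, d_i events among r_i at risk, and g = Σ d_i / [r_i(r_i − d_i)]:

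- plain limits: s ± 1.96 · s√g
- log(-log) limits: apply ± 1.96 · √g / |ln s| to ln(−ln s), then transform back

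Without censoring, s = x/n with x binomial (n, S), and s√g = √[s(1−s)/n], so coverage is exact. Samples with s equal to 0 or 1 count as misses for both methods.

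**One case by hand: n=17, 16 patients event-free, true S=0.8**

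- s = 16/17 = 0.941; SE = √(0.941 × 0.059/17) = 0.057.
- Plain: 0.941 ± 0.112 gives 82.9% to 105.3%. It misses 80% and passes 100%.
- Log(-log): ln(−ln s) = −2.803, half-width 1.96 × 1.000, giving 65.0% to 99.2%. It covers 80%.

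Over all outcomes at n=17 and S=0.8, the plain interval covers when x = 10 to 15 (probability 87.1%), and the log(-log) interval when x = 11 to 16 (94.0%). Plain limits leave 0-100% when x is 1 to 3 or 14 to 16 (52.6%).

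**Results.** Uncensored rows are exact. Rows with 0-40% censored by the time point come from 20,000 simulated samples per cell. Rows with an annual rate are simulated to year 10.

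| n | S | Censoring | Plain | Log(-log) | Plain limits outside 0-100% |
|---|---|---|---|---|---|
| 17 | 0.2 | none | 87.1% | 96.7% | 52.6% |
| 17 | 0.8 | none | 87.1% | 94.0% | 52.6% |
| 17 | 0.4-0.6 | 0-40% | 90.3-92.0% | 94.2-95.7% | 5-15% |
| 17 | 0.1 or 0.9 | none | 82.9% | 81.1% | 75.1% |
| 38 | 0.9 | none | 89.4% | 95.0% | 44.7% |
| 69 | 0.9 | none | 91.6% | 95.4% | 7.6% |
| 69 | 0.9 | 10%/yr | about 89% | about 95-96% | about 36% |
| 60, 69 | 0.2-0.8 | 0-40% | 92.3-94.4% | 93.5-96.2% | 0-3.5% |
| 60, 69 | 0.8 | 20%/yr | about 85-87% | about 92-93% | about 21-30% |

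A hazard of 10% per year would censor 1 − e^(−1) = 63% of event-free patients by year 10; 20% per year would censor 1 − e^(−2) = 86%. These are stress cases, not document figures.

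**Brookmeyer-Crowley.** For the median, 0-40% censored:

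| n | Linear | Log(-log) |
|---|---|---|
| 60-69 | 93.9-94.7% | 95.0-96.0% |
| 35-38 | 92.9-96.1% | 93.8-95.3% |
| 17 | 90.9-95.0% | 95.4-96.9% |

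**The case against.** **The plan does not say untransformed.** A reader might infer that SAP 8.1.4 prescribes plain Greenwood limits. It does not; Greenwood's variance serves plain and transformed intervals alike. This stands as a limit on the claim. The inference is still the natural one, because the section names its scale both for Brookmeyer-Crowley and for cumulative incidence. If plain limits are not meant, the method is undefined, and the same sentence is needed.

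**The small sample sizes are weakly sourced.** The counts 17 and 38 come from evaluable-set response by Week 48. SAP duration of response uses full-analysis-set responders with no Week 48 limit, and K-M for that endpoint is conditional on most transferred responders staying on treatment until progression or loss. Overall survival and PFS use whole cohorts. Advanced-phase sizes by line, numbers at risk at year 10 and advanced-phase survival rates are not given. All of this stands, so the small-n rows are illustrations. The chronic-phase groups are much larger (288 second-line, 250 first-line bosutinib), and no harm is shown there.

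**Nothing depends on the intervals.** SAP 4.2 makes them descriptive, and event counts, censored patients and listings are also reported. This stands and sets the severity.

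**The remedy fails where coverage is worst.** At n=17 with S=0.1 or 0.9, log(-log) covers 81.1%, no better than plain, because 16.7% of samples give an estimate of exactly 0 or 1. This stands too.

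**Conclusion.** The point holds, at low severity. On the natural reading of SAP 8.1.4, K-M yearly-rate intervals fall short of 95% in small subsets, at rates near 0 or 1, or under heavy censoring, and in the smallest or most extreme of these settings many limits are impossible values. Log(-log) limits largely cure this except where the estimate is itself 0 or 1.

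Two stronger readings are not supported. A reader might infer that advanced-phase intervals in general cover well below 95% and often leave 0-100%. At the documented cohort sizes, S=0.2-0.8 and light to moderate censoring, coverage is about 92-95% and at most 3.5% of intervals leave the range. A reader might also extend both defects to Brookmeyer-Crowley. Its limits are times, so the 0-100% issue cannot arise, and its median coverage is about 91-96%; quartile coverage was not calculated.

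The sizes rest on assumed survival rates, exponential times and assumed censoring.

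**What to change.** In SAP 8.1.4, state that confidence intervals for K-M yearly rates use Greenwood's variance with the log(-log) transformation. For consistency, specify log(-log) Brookmeyer-Crowley intervals for medians and quartiles. Report the number at risk beside each yearly rate, so that sparse late estimates can be seen as such.

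The cost is a sentence in the SAP and a software option. Some intervals become asymmetric or slightly wider. The change does not help where the K-M estimate is exactly 0 or 1; there the number at risk carries the information.
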